10.2 Monitoring of Study Sites

Site monitoring will be performed based on the Monitoring Plan. Site monitoring will occur on a regularly scheduled basis and, as needed, based on site performance and perceived training needs. The purpose of such monitoring will be to ensure that the study is being conducted in accordance with the protocol, particularly through helping study site staff resolve any local problems and providing extra training focused on specific needs. Particular attention will be given to the effectiveness of strategies to recruit appropriate participants, the completeness of follow-up, the maintenance of participant adherence to study treatment, and the reporting of study outcomes and collection of relevant supporting documentation. Details are provided in the Monitoring Plan.

11. Data Analysis Plan

Further details can be found in the Statistical Analysis Plan (SAP).

11.1 Analysis Sets

- a) The On-Treatment Analysis Set will consist of all randomized patients who received at least one dose of study drug. However, only those events/observations occurring during therapy with the randomized treatment strategy or within 3 days of the last dose of randomized treatment will be a part of this analysis set. A transition in randomized treatment as defined in Section 7.4 is not considered a deviation in therapeutic strategy and observations occurring after the transition will be a part of this analysis set. Crossovers and permanent discontinuations (Section 7.7) of randomized treatment are considered an end to the randomized anticoagulant or antiplatelet therapeutic strategy; only observations occurring up to 3 days after crossovers or discontinuations of randomized treatment will be a part of this analysis set. The primary assessment for efficacy outcomes will be analyzed based on the On-Treatment Analysis Set.
- b) The Intention-to-Treat Analysis Set will consist of all randomized patients with the exception of those who did not qualify for randomization and did not receive study drug but were inadvertently randomized into the study. Following the intention-to-treat

principle, patients will be analyzed according to the treatment group to which they were assigned at randomization. Additional assessments for efficacy outcomes will be analyzed based on the Intention-to-Treat Analysis Set.

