Study sites and number of subjects planned

The study will be conducted at approximately 30 sites in the United States. It is estimated that approximately 750 patients will be enrolled during a recruitment period of approximately 6-12 months. Each participant will be followed through 28 days or hospital discharge, whichever comes first.

Study Initiation	Phase of development
Estimated date of first subject enrolled	Q2 2020

Study Design

This is a multicenter, open-label, 2x2 factorial, randomized-controlled trial in critically-ill patients with novel coronavirus disease 2019 (COVID-19) evaluating the efficacy and safety of full-dose vs. standard prophylactic dose anticoagulation and of antiplatelet vs. no antiplatelet therapy for prevention of venous and arterial thrombotic events. The trial will follow the principles of a prospective randomized open blinded end-point (PROBE) design.

Study Objectives

Primary Efficacy Objective:	Primary Efficacy Outcome Measure:
To assess the efficacy of: 1) full-dose anticoagulation (FDAC) versus standard-dose prophylactic anticoagulation (SDPAC) and 2) antiplatelet (AP) therapy versus no AP therapy on venous or arterial thrombotic events in critically-ill patients with COVID-19.	The hierarchical composite endpoint of: 1. Death due to venous or arterial thrombosis 2. Pulmonary embolism 3. Clinically evident deep venous thrombosis (DVT) 4. Type 1 myocardial infarction (MI) 5. Ischemic stroke 6. Systemic embolic event (SEE) or acute limb ischemia (ALI) 7. Clinically silent DVT

Key Secondary Efficacy Objective:	Key Secondary Efficacy Outcome Measure:
To assess the efficacy of: 1) FDAC versus SDPAC and 2) AP therapy versus no AP therapy on clinically evident venous or arterial thrombotic events in critically-ill patients with COVID-19.	The hierarchical composite endpoint of: 1. Death due to venous or arterial thrombosis 2. Pulmonary embolism 3. Clinically evident DVT 4. Type 1 MI 5. Ischemic stroke 6. SEE or ALI

Primary Safety Objective:	Primary Safety Outcome Measure:
To evaluate the safety of: 1) FDAC versus SDPAC and 2) AP therapy versus no AP therapy in critically-ill patients with COVID-19.	Composite endpoint of fatal or life-threatening bleeding

Target Population

Patients with COVID-19 requiring intensive care unit (ICU) admission (critically-ill) without an indication for full-dose anticoagulation.

Inclusion Criteria (See Section 6 for additional details)

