7.3 Duration of Randomized Treatment: The study allocated regimen should be continued until hospital discharge (including after ICU discharge) or through 28 days post-randomization, whichever occurs first.

7.4 Transition in Randomized Treatment Assignment: The investigator may transition between acceptable regimens within the randomized treatment assignment as deemed appropriate clinically (e.g., transition from enoxaparin to subcutaneous heparin for SDPAC in the setting of new or worsening renal failure). Transitions to direct thrombin inhibitors, or fondaparinux are permitted if heparin-induced thrombocytopenia is confirmed or suspected. After a patient is transferred out of the ICU, transitions to oral anticoagulation are also permitted in the absence of significant renal or hepatic dysfunction (see Protocol Appendix for further details). Transitions in anticoagulant therapy will be recorded in the

eCRF. Refer to the Appendix for further guidelines regarding transitions in randomized treatment assignment including acceptable alternative regimens.

7.5 Blinding: Treatment will be open-label without blinding.

7.6 Concomitant Medications: All non-antithrombotic therapy is at the discretion of the patient's treating physicians. Non-study anticoagulant or antiplatelet therapy is not permitted while receiving the study allocated regimen unless there is a change in the patient's clinical status requiring an alternative regimen.

7.7 Discontinuation of Study Drug: Patients and healthcare providers may voluntarily discontinue study drug for any reason at any time. If adverse events occur that are believed to be due to study drug, or safety events occur that, in the opinion of the investigator, contraindicate further dosing of study drug, study drug may be temporarily interrupted or permanently discontinued. Whenever possible, restarting study drug should be encouraged, so long as the investigator judges that the potential benefit outweighs the risk. Situations that warrant temporary or permanent study drug discontinuation include:

- Active clinically significant bleeding
- Acute hemorrhagic or ischemic stroke at meaningful risk for hemorrhagic transformation
- Severe thrombocytopenia (platelet count <50,000)
- Evidence of overt disseminated intravascular coagulation (e.g. fibrinogen levels <150 mg/dl or INR >2.9 despite adequate vitamin K repletion). See Manual of Site Operations for guidelines to help discriminate DIC from sepsis induced coagulopathy.

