3. Clinically evident DVT
4. Type 1 MI
5. Ischemic stroke
6. SEE or ALI

Secondary Efficacy Outcomes

- Composite of venous thrombotic events (PE or clinically evident or silent DVT)
- Composite of arterial thrombotic events (ischemic stroke, SEE or ALI, or T1MI)
- Each of the individual components of the primary efficacy outcome
- Cardiovascular death

Exploratory Efficacy Outcomes

- Clinical improvement on COVID ordinal scale recommended by WHO R&D Blueprint Group
- Ventilator-free days (at 28 days post-randomization)
- Time from ICU admission to ICU discharge
- Acute kidney injury
- Need for new renal replacement therapy
- Pulseless electrical activity cardiac arrest
- Catheter thrombosis
- Myocardial dysfunction
- All-cause mortality

Safety Outcomes

Primary Safety Outcome

Time to first occurrence of fatal or life-threatening bleeding

Secondary Safety Outcome

- GUSTO moderate or severe bleeding

9. Study Procedures

Screening and Randomization

- Obtain written informed consent from patient or legal authorized representative
- Review inclusion/exclusion criteria (including pregnancy testing for women of child bearing potential), relevant medical history, vital signs (including weight), and medications
- Review or obtain labs (platelet count, INR and fibrinogen)
- Randomize (Day 0) using the Interactive Web Randomization System (IWRS)
- Initiate randomized anticoagulant strategy and, if applicable, antiplatelet therapy

Follow-up (through day 28 or hospital discharge, whichever occurs first)

- Continue randomized antithrombotic therapy
- Monitor anticoagulation as per local practice; obtain INR daily and fibrinogen at least every 3 days while receiving ICU-level care (see Appendix for details)
- Obtain bilateral lower extremity venous ultrasound as a single assessment any time between days 10-14. If a patient crosses over or discontinues randomized anticoagulation strategy on Day 4 through Day 9, this assessment should be performed as close to the date of discontinuation as possible (and no longer than 3 days after discontinuation). For crossover or permanent discontinuation prior to Day 4, this assessment is not required.
- Assess for efficacy and safety events

Additional details about study operations can be found in the Manual of Site Operations

10. Site Training and Monitoring

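### Section 11.1 makes on-treatment the primary set for every efficacy outcome, mortality and 28-day ventilator-free days included; ITT should be the main set for the non-thrombotic ones

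*Combined protocol and SAP*

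**What the plan says.** Section 11.1(a) defines the On-Treatment set as randomized patients with at least one dose of study drug, and admits "only those events/observations occurring during therapy with the randomized treatment strategy or within 3 days of the last dose of randomized treatment". A transition between acceptable regimens does not close the window. Crossover and permanent discontinuation do: "only observations occurring up to 3 days after crossovers or discontinuations of randomized treatment will be a part of this analysis set". The paragraph ends: "The primary assessment for efficacy outcomes will be analyzed based on the On-Treatment Analysis Set". Section 11.1(b) gives ITT the second role: "Additional assessments for efficacy outcomes will be analyzed based on the Intention-to-Treat Analysis Set".

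Section 8 places cardiovascular death among the secondary efficacy outcomes. Under "Exploratory Efficacy Outcomes" it lists all-cause mortality (no time point), the WHO ordinal scale, time to ICU discharge, acute kidney injury, new renal replacement therapy and "Ventilator-free days (at 28 days post-randomization").

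Section 7.7 lists situations that warrant temporary or permanent discontinuation, among them "Active clinically significant bleeding", severe thrombocytopenia and overt DIC. It keeps all study assessments going after drug is stopped. On follow-up, the synopsis says: "Each participant will be followed through 28 days or hospital discharge, whichever comes first".

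**The concern.** Mortality, ventilator-free days and time to ICU discharge describe a patient's whole course over a fixed horizon. A set that closes 3 days after treatment ends cannot show that course for patients who stop early. Those patients are unlikely to be a random sample: bleeding, thrombocytopenia and DIC plausibly predict death and longer ventilation, and so does a thrombotic event that leads a control patient to cross over.

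The two factorial comparisons may also be truncated differently. Section 11.1 ends the anticoagulant or the antiplatelet strategy. A clopidogrel patient who bleeds can discontinue, whereas a patient allocated to no antiplatelet therapy has no dose to stop, so on a natural reading that window closes only at crossover.

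At stake is which result the trial report presents as its primary assessment of mortality and ventilator-free days. Under the present wording it is the one without the later in-hospital deaths.

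**Working it through.** **1. The plan's own figure.** Section 11.5 gives at least 170 events for at least 80% power at a hazard ratio of 0.65, two-sided alpha 0.05, 1:1 allocation. Schoenfeld: 4 × (1.960 + 0.842)² / (ln 0.65)² = 31.40 / 0.1856 = 169.2, so 170 events; power at 170 events is 80.2%. The figure reproduces. It concerns the thrombotic composite and is not affected by this point.

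**2. Scope of the rule.** Section 11.1 speaks of efficacy outcomes without limit, and Section 8 classes the outcomes above as efficacy outcomes. Section 11.2 names only the primary composite when it describes the primary on-treatment comparison, but it does not narrow Section 11.1, and Section 11.2 extends analogous analyses to the secondary and exploratory time-to-event outcomes.

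**3. Window for a patient still in hospital.** Last counted day = min(28, end day + 3); uncounted days = 28 − last counted day.

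| Strategy ends on day | Last counted day | Uncounted days of 28 |
|---|---|---|
| 4 | 7 | 21 |
| 6 | 9 | 19 |
| 9 | 12 | 16 |
| 14 | 17 | 11 |
| 24 | 27 | 1 |
| 25 or later | 28 | 0 |

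A complete 28-day value needs the strategy to continue to Day 25 or later. Patients treated until discharge or Day 28 lose nothing that is collected, because Section 7.3 ends treatment at the same point as follow-up.

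**4. How many deaths could fall outside (assumed inputs).** The documents give no discontinuation or crossover rate. Assume 10% all-cause mortality by Day 28 at constant hazard (borrowing the 10% competing mortality of Section 11.5, for which no horizon is stated), patients in hospital to Day 28, the same hazard after stopping, and a fraction s due to stop on day d. Then h = −ln(0.90)/28 = 0.00376 per day, and deaths outside the window = 750 × s × [exp(−h(d + 3)) − 0.90], out of 750 × 0.10 = 75.

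- s = 10%, d = 14: 750 × 0.10 × (0.938 − 0.900) = 2.9 deaths, 4% of 75.
- s = 20%, d = 9: 8.4 deaths, 11%.
- s = 40%, d = 4: 750 × 0.40 × (0.974 − 0.900) = 22.2 deaths, 30%.

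This shows how much information could leave the set. It is not an estimate of bias between arms.

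**5. Direction.** Bleeding-related stopping is plausibly commoner on full-dose anticoagulation or clopidogrel and would truncate those arms. Both crossover examples in Section 7.7 are control patients: standard-dose patients who develop atrial fibrillation or DVT, and no-antiplatelet patients with an acute coronary syndrome. These truncate the control arms. The documents do not allow the two to be netted.

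**The case against.** The strongest reply is that nothing is lost to the trial. Sections 11.1(b) and 11.2 plan ITT comparisons, and Section 7.7 keeps collecting data. A reader might infer that later deaths and ventilator days are discarded, or that 28-day values cannot be derived at all. The documents do not support that: it is true only inside the On-Treatment set. What remains is which of two planned analyses is designated primary.

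A reader might also infer that the rule favours the experimental arms and attach a mortality ratio to it. The documents do not support this either. Control-arm crossover pulls the other way, and any ratio depends on how truncated patients are handled. For example, assume true mortality of 20% in both arms, 30% v 20% stopping, and 20% of stoppers dying late. Counting truncated patients as survivors gives 14% v 16%, a ratio of 0.88. Censoring them early gives about 14/70 v 16/80, that is 20% v 20%, a ratio near 1.00. Bleeding harm is also not hidden: fatal or life-threatening bleeding is the primary safety outcome, and the on-treatment sentence concerns efficacy.

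Three further points stand in part. Most of these outcomes are exploratory, so no confirmatory claim rests on them, though cardiovascular death is secondary. The protocol defers detail to an SAP whose separate text is not in the material supplied. It may set another rule, but Section 11.1 as written would then need to agree with it. Finally, unobserved days after discharge come from the end of follow-up, affect ITT equally, and should not be blamed on the on-treatment rule.

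**Conclusion.** The point holds as a matter of designation. As written, the primary assessment of cardiovascular death, all-cause mortality, ventilator-free days, ICU discharge, renal outcomes and the ordinal scale omits in-hospital observations more than 3 days after the strategy ends. A 28-day value in that set is incomplete for an inpatient whose strategy ends before about Day 25. This follows from the text and needs no assumption.

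That the result can be biased rests on two plausible premises: the reasons for stopping or crossover are prognostic, and their frequency can differ by arm. Direction and size cannot be given. The 4–30% of deaths outside the window holds only under the assumptions in step 4. The primary composite and its power are untouched. The change should be made, since it is cheap and removes a weak primary reading of mortality. It does not threaten the trial's main conclusion.

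**What to change.** In Section 11.1, and matching it in the SAP:

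- Limit the on-treatment primary assessment to the thrombotic outcomes: the primary and key secondary composites, their components, and the venous and arterial composites.
- Name the Intention-to-Treat set as the main set for all-cause mortality, cardiovascular death, ventilator-free days, time to ICU discharge, renal outcomes and the ordinal scale, with on-treatment as supportive.
- Label mortality as in-hospital through Day 28.
- State the scoring of ventilator-free days: death by Day 28 scores 0, plus an explicit assumption for days after discharge (for instance, ventilator-free if discharged alive off the ventilator, ventilated if discharged on one).

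The cost is wording. In-hospital data after stopping are already collected; days after discharge are not, so those values rest on the stated assumption. The downsides are that these outcomes use a different main set from the composite, that time after stopping dilutes a pure drug effect, and that thrombotic death (on-treatment, as a component) and cardiovascular death (ITT) would sit in different sets, which the tables should label.

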11.2 Analyses

The primary efficacy analysis will be performed using the On-Treatment Analysis Set. The primary efficacy assessments will involve on-treatment comparisons of the effect of allocation to: 1) FDAC versus SDPAC (pooled across AP regimens); and 2) AP therapy versus no AP therapy (pooled across anticoagulation regimens) on the primary composite endpoint of death due to venous or arterial thrombosis, pulmonary embolism, clinically evident DVT, type 1 MI, ischemic stroke, SEE or ALI, or clinically silent DVT through the follow-up period. Clinical event rates will be calculated according to the cumulative incidence function. Intention-to-treat comparisons will also be performed as additional analyses.

The primary analysis will be conducted by estimating the unmatched win ratio by comparing 1) every participant in the FDAC arm to every participant in the SDPAC arm to determine a winner, and 2) every participant in the AP therapy to every participant in the no AP therapy arm to determine a winner. The estimated win ratio (the total number of wins in the FDAC arm divided by the total number of wins in the SDPAC arm, and the total number of wins in the AP therapy arm divided by the total number of wins in the no antiplatelet therapy arm) will be calculated evaluating the composite in a hierarchical manner. A win ratio greater than 1 will be in favor of the FDAC arm and AP therapy arm, respectively.

The corresponding two-sided 95% confidence intervals will be calculated. The analysis will be performed using the unmatched pair win ratio approach.²³ For the comparison of FDAC vs. SDPAC, the analysis will be stratified by ongoing or planned AP therapy and the second factorial treatment comparison of AP therapy vs. no AP therapy for those eligible. For the analysis of AP therapy vs. no AP therapy, the analysis will be stratified by FDAC vs. SDPAC randomization. Contributions of each component of the composite endpoint to total number of winners used in estimation of the win ratio will be reported.

In a secondary analysis of the primary composite endpoint, differences in clinical outcomes between the treatment groups will be assessed using the Gray's test for equality of cumulative incidence functions, incorporating stratification in the analysis as outlined for the primary analysis. Hazard ratios and 95% confidence intervals will be calculated using a Fine-Gray model to account for the competing risk of mortality. Analogous analyses will be performed for the secondary and exploratory efficacy outcomes involving time-to-event comparisons. Additional details of the analytic approach can be found in the Statistical Analysis Plan (SAP).

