This is a phase 4, multicenter, open-label, 2x2 factorial, randomized-controlled trial using a PROBE design. The trial will be conducted in approximately 30 sites in the United States. Approximately 750 patients will be enrolled. Patients will be randomized in a 1:1 allocation ratio to receive either FDAC or SDPAC. In patients without an ongoing indication for AP therapy at baseline, a second randomization will be performed in a 1:1 allocation ratio to either AP or no AP therapy. Randomization to FDAC vs. SDPAC will be stratified by whether or not the patient is planned to receive non-study AP therapy and therefore would not qualify for randomization in the second factorial treatment comparison. Patients will be assessed clinically and with bilateral lower extremity venous ultrasound between 10 and 14 days post-randomization. Patients will be followed through hospital discharge or 28 days, whichever occurs first, for a maximum follow-up of 28 days. The anticipated total duration of the study is 6-12 months.

6. Study Population

Inclusion Criteria

Patients must meet all the following criteria to be eligible for enrollment:

1. Age \geq 18 years (male or female)
2. Acute infection with severe acute respiratory syndrome coronavirus 2 (SARS-CoV2)*
3. Currently admitted to an intensive care unit (ICU)**

**Acute SARS-CoV2 infection is defined as a documented, positive SARS-CoV2 RT-PCR, SARS-CoV2 IgM antibody test, or other accepted assay (see Manual of Site Operations) with active respiratory signs or symptoms during the current hospitalization.*

***Where ICU admission occurred \leq 96 hours prior to randomization. ICU admission also includes patients requiring ICU-level care in other units. Criteria for ICU-level of care are defined in the Protocol Appendix.*

Exclusion Criteria

Patients who meet any of the following criteria are excluded from the study:

1. Ongoing (>48 hours) or planned full-dose (therapeutic) anticoagulation for any indication
2. Ongoing or planned treatment with dual antiplatelet therapy
3. Contraindication to antithrombotic therapy or high risk of bleeding due to conditions including, but not limited to, any of the following:
 - a) History of intracranial hemorrhage, known CNS tumor or CNS vascular abnormality
 - b) Active or recent major bleeding within the past 30 days with untreated source
 - c) Platelet count $<$ 70,000 or known functional platelet disorder
 - d) Fibrinogen $<$ 200 mg/dL

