11.5 Sample Size Considerations

The sample size is based on the secondary analysis of the primary efficacy endpoint. With a 2-sided alpha of 0.05, a 40% event rate in the control arm rate in the group receiving both SDPAC and no AP therapy (estimated based on 3 recent case series of critically-ill patients with COVID-19),⁶⁻⁸ a 10% competing risk of mortality, and a 1% dropout rate (e.g., withdrawal of consent, loss-to-follow-up), approximately 750 patients should provide at least 170 events and therefore at least 80% power to detect a 35% relative risk reduction (RRR) for the FDAC vs. SDPAC comparison using Gray's test for equality of cumulative incidence function. The power for the AP therapy comparison is expected to be slightly less (~70%) as it is assumed that 10% of patients will not be eligible for the AP randomization. The approach of powering the trial based on the secondary analysis of the primary efficacy endpoint (i.e., cumulative incidence function) is expected to be conservative with respect to the primary analysis of the primary efficacy endpoint (i.e., unmatched win ratio), for which larger power is expected.

During the course of the trial, trial leadership will monitor the aggregate event rate and proportion of patients who proceed to the second randomization to ensure consistency with the initial assumptions and preserve the planned power for the trial. The target sample size may be increased to ensure accrual of an adequate number of efficacy endpoint events to preserve the overall initial planned power. Refer to the SAP for further details.

12. Data and Safety Monitoring and Review

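### Does naming only mortality as a competing risk distort the secondary event rates, given that follow-up ends at discharge?

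*Combined protocol and SAP*

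**What the plan says.** Section 5 fixes the end of observation: "Patients will be followed through hospital discharge or 28 days, whichever occurs first". The Synopsis and the follow-up list in Section 9 say the same.

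Section 11.2 makes the unmatched win ratio the primary analysis. For absolute rates it says: "Clinical event rates will be calculated according to the cumulative incidence function". The secondary analysis of the composite uses Gray's test, followed by this: "Hazard ratios and 95% confidence intervals will be calculated using a Fine-Gray model to account for the competing risk of mortality". The same approach extends to the secondary and exploratory time-to-event outcomes. Section 11.2 then refers the reader to the SAP for more detail.

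Section 11.5 sizes the trial on this secondary analysis and assumes "a 10% competing risk of mortality, and a 1% dropout rate". Its examples of dropout are withdrawal of consent and loss to follow-up. The Synopsis adds one timing figure: the 40% control rate is given at a median follow-up of 14 days.

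Section 11.1 creates a further exit in the On-Treatment set: "only observations occurring up to 3 days after crossovers or discontinuations of randomized treatment will be a part of this analysis set".

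Nothing in the protocol text says whether a patient discharged alive without an event is censored, counted as having a competing event, or kept in the risk set as event-free to Day 28. No separate SAP text was available to this review.

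**The concern.** In a trial whose follow-up ends at discharge, going home alive is the commonest way out. A median follow-up of 14 days against a 28-day maximum implies that about half the patients leave observation by Day 14, and with 10% competing mortality many of those exits must be live discharges. The plan names the smaller exit and is silent on the larger.

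If silence meant censoring, the cumulative incidence curve would give discharged patients the later risk of those still in hospital. The estimate would answer a hypothetical question (risk by Day 28 if nobody were discharged), and only if discharge were unrelated to thrombotic risk. A reader would probably take it as the proportion of patients with an in-hospital event and read it too high. Absolute differences between arms would be stretched as well.

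The scan schedule sharpens this. Section 9 says: "Obtain bilateral lower extremity venous ultrasound as a single assessment any time between days 10-14". It names crossover and discontinuation, but not discharge, as triggers for an earlier scan. A patient who leaves before Day 10 is not scanned, and censoring would give that patient the silent-DVT yield of those who stayed.

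**Working it through.** **Plan's own figure.** Events needed for a hazard ratio of 0.65, 1:1 allocation, two-sided alpha 0.05 and 80% power (Schoenfeld): 4 × (1.960 + 0.842)² / (ln 0.65)² = 169.2, rounded up to 170. Power with 170 events is 80.2%. The stated 170 reproduces, and the formula contains no term for how discharge is coded.

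**Inputs for the illustration.** From the documents: 40% control event rate, 10% competing mortality, hazard ratio 0.65, Day 28 limit, 14-day median follow-up. Assumed: the shape of the event hazard and the discharge hazard, because the documents give neither. The 14-day median stay is also an assumption. It fits the median follow-up but is not the same quantity, since deaths also end follow-up.

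**Constant hazards per day.**
- Event: −ln(0.6)/28 = 0.01824
- Death: −ln(0.9)/28 = 0.00376
- Live discharge: ln(2)/14 = 0.04951

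Day 28 incidence = (event hazard / total hazard) × (1 − exp(−28 × total hazard)).

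- Discharge censored, death competing: (0.01824/0.02201) × (1 − 0.54) = 38.1%.
- In hospital, discharge and death both competing: (0.01824/0.07152) × (1 − 0.135) = 22.1%.
- Ratio: 38.1/22.1 = 1.73. In this case 60% leave alive and event-free and 4.6% die first.

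**Other shapes, by numerical integration at a 14-day median stay.**

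| Event hazard | Discharge starts | Censored | In hospital | Ratio |
|---|---|---|---|---|
| Constant | Day 0 | 38.1% | 22.1% | 1.73 |
| Decaying, 7-day mean | Day 0 | 39.2% | 30.6% | 1.28 |
| Decaying, 7-day mean | Day 7 | 39.2% | 35.0% | 1.12 |

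Over median stays of 10 to 20 days the ratio runs from 1.07 to about 2.1. Placing half the events at a Day 12 scan gives 1.3 to 1.8 at 14 days. If instead 40% is taken as the in-hospital rate, with 10% in-hospital deaths and a 14-day median time to death or discharge, the censored figure is 59%.

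**Absolute difference at hazard ratio 0.65.**
- Constant hazard: censored 38.1 − 26.9 = 11.2 points; in hospital 22.1 − 15.3 = 6.8 points.
- Decaying hazard, discharge from Day 7: 39.2 − 27.6 = 11.5 points (from unrounded values); 35.0 − 24.5 = 10.5 points.

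**The third coding.** Suppose discharged patients are kept in the risk set, event-free, to Day 28, and nothing else is censored. The curve at Day 28 is then events divided by all patients, which is the in-hospital figure (22.1%, 30.6% or 35.0%), and the excess is zero. Mortality can still be the only competing risk named.

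**What counting discharge in the rate does to the comparison.** With no treatment effect and discharge 1.5 times faster in one arm, that arm's in-hospital rate falls from 22.1% to 17.7% (4.4 points), or from 35.0% to 33.8% (1.2 points). The censored rate does not move. In a simulation of 742 patients under constant hazards (40% in-hospital events), no treatment effect and 25% faster discharge in one arm, Gray's test rejected in about 14% of trials with discharge competing (hazard ratio about 0.91) and about 5% with discharge censored (hazard ratio about 1.00).

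**The case for a change.** The strongest argument for a change is that the choice can move a published rate by more than the treatment effect, costs one sentence to state, and, in an open-label trial, is better settled before the data are seen. The same method also serves the secondary and exploratory outcomes. The gap in the text is real, and so is the arithmetic on the censored reading.

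Three things weaken it. First, censoring is an inference: naming mortality as a competing risk does not say what happens at discharge, and holding patients event-free is compatible with the same words. Second, the coding of exits is ordinary SAP content, and Section 11.2 sends the reader there. Third, the specific remedy is to show in-hospital incidence while keeping the tests discharge-censored. It would separate the displayed curves from the Gray's test meant to compare them. It would make displayed rates depend on length of stay, which clinicians who know the allocation can influence. It would also still censor On-Treatment patients 3 days after they stop, so those rates would not be simple in-hospital proportions either.

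What stands is that a report should say what its rates estimate.

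**Conclusion.** No change to the plan follows. The concern identifies an unstated coding rule, not a wrong one. If discharge were censored, the secondary rates would exceed in-hospital incidence by a factor of about 1.1 to 1.7 at a 14-day median stay; this rests on assumed hazard shapes and on discharge being unrelated to risk. If discharged patients are held event-free to Day 28, there is no excess. Either coding is defensible once labelled. Censoring estimates a hypothetical risk and protects the comparison from unequal lengths of stay; the in-hospital rate is simpler to read but gives up that protection.

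The stakes are limited. The win ratio does not use the cumulative incidence function, and the 170 events reproduce whichever coding is used. With equal discharge in both arms and a true hazard ratio of 0.65, the simulation gave a Fine-Gray hazard ratio of about 0.66 (censored) or 0.68 (competing). An analyst can settle the coding in the SAP and label the rates accordingly.
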